#### **Document History**

Version	Issue Date	Changes	
1.2	7-Aug-2015	Final approved version	
2.0	20-Nov-2015	
 
Minor changes in wording to improve clarity
 
	
		
 
Changed primary care Day2 visit window to 40-56 hours
 
	
		
 
Changed Day28 visit window to -3/+7 days
 
	
		
 
Added assessment of febrile illness at Day28
 
	
		
 
All participants to receive gift vouchers at Day28
 
	
		
 
Participants will be asked to consent to remain in the study if they lose
 
	
		capacity. Proxy assent will also be sought in these cases	
		For full details see:	
		MERMAIDS_Protocol_ARI_V2.0_summary_of_changes.docx	
3.0	11-Mar-2016	• Inclusion criteria: added 'dyspnoea' as an eligible respiratory symptom for	
		both primary and secondary care	
		• Exclusion criteria: Patient is enrolled in an interventional clinical study of an anti-infective or immunomodulatory therapy	
		• Delay of Day 2 blood sample collection up to Day 4 will be permissible.	
		• Clarified that participants may be followed up in a hospital, GP or	
		outpatient clinic, at home or at work	
		For full details see:	
		MERMAIDS_Protocol_ARI_V3.0_summary_of_changes.docx	
4.0	11-May-2016	
 
Day 28 visit window extended to -3/+21 days
 
	
		
 
Added exclusion criterion: previous enrolment in MERMAIDS-ARI
 
	
5.0	06-Apr-2020	
 
Removal of exclusion criteria: "Patient is enrolled in an interventional
 
	
		clinical study of an anti-infective or immunomodulatory therapy"	
		
 
Addition of section 7.2.3 Study consenting procedures during the SARS-
 
	
		CoV-2 pandemic	
6.0	15-May-2020	
 
Increased duration of symptom onset to admission from 7 days to 14 days
 
	

# 1. SYNOPSIS

Study Title	Multi-centre EuRopean study of MAjor Infectious Disease Syndromes (MERMAIDS): Acute Respiratory Infections in Adults	
Ref. no. / short title	MERMAIDS – ARI	
Study Design	Prospective, observational study	
Study Participants	Adults (≥ 18 years old) with a suspected community acquired acute respiratory tract infection, Group 1: attending primary care Group 2: admitted to hospital	
Planned Sample Size	Primary Care patients (Group 1): n = 750 Hospitalised Patients (Group 2): n = 2,250	
Planned Study Period	60 months	

	Objectives	Outcome measures
Primary objective	Identify host and pathogen related determinants of severity of community acquired acute respiratory infections (ARI) in adults.	Differentially expressed host genes (≥ 2- fold difference in expression levels) as assessed by RNA transcriptome microarray in hospitalised and primary care managed cases of ARI, stratified by pathogen* and comorbidity**. *Influenza virus, Human Rhinovirus, Respiratory Syncytial Virus, Streptococcus pneumoniae ; **No comorbidity, chronic pulmonary disease, chronic cardiovascular disease, chronic metabolic disease (diabetes)
Secondary objectives	Describe the aetiology, clinical management and outcomes of adult patients with community acquired ARI, in both primary care and hospital care, across Europe.	
 
In both groups:
 
Prevalence of detection of putative pathogens in respiratory tract samples
 
Proportion of cases receiving antibiotics, antivirals, antifungals and/or immunomodulators.
 
28 day mortality
 
Additional in group 1 (primary care):
 
Proportion of cases requiring hospitalisation
 

	Objectives	Outcome measures
		
 
Additional in group 2 (hospitalised patients):
 
Severity of illness at enrolment as assessed by Pneumonia Severity Index (PSI) and CURB-65
 
Proportion of cases requiring during
 

		admission: supplemental oxygen; non- invasive or invasive mechanical ventilation; extra-corporeal life support.
		
 
Duration of invasive mechanical ventilation and extra-corporeal life support, if applicable
 

		
 
Proportion of cases requiring Intensive Care Unit (ICU)/High Care Unit (HCU) admission
 

		Hospital - and ICU/HCU length of stay
		In-hospital mortality
Tertiary Objectives	To develop and validate prognostic and diagnostic algorithms.	This is an exploratory objective. Some measures that could be included in algorithms are classifier gene sets based on host gene expression profiles, pathogen profiles, demographics, co- morbidities, risk factors, and clinical parameters. The diagnostic/prognostic algorithms will be evaluated for their ability to correctly diagnose infecting pathogen and/or predict adverse outcome in ARI.
	To gain understanding into pathophysiological mechanisms contributing towards development of severe disease.	This is an exploratory objective to increase pathophysiological insights by integrative (systems medicine) analyses of pathogen- and patient characteristics. Measures that will be included in these integrative analyses are host gene expression profiles, clinical data on disease progression/outcome, deep sequencing of pathogen genomes and microbiomes.

PREPARE | Multi-centre EuRopean study of MAjor Infectious Disease Syndromes

8

9

# 2. ABBREVIATIONS

ARI	Acute respiratory infection
CI	Chief Investigator
CRF	Case Record Form
CRO	Contract Research Organisation
CURB-65	Severity Score (Confusion, Urea, Respiratory rate, Blood pressure, Age >65y)
DAVID	Database for Annotation, Visualization, and Integrated Discovery
DM	Data Management
eCRF	Electronic Case Record Form
EDC	Electronic data capture
EDTA	Ethylenediaminetetraacetic acid
FDR	False Discovery Rate
GCP	Good Clinical Practice
GO	Gene Ontologies
GSEA	Gene Set Enrichment Analysis
HRV	Human Rhinovirus
ICH	International Conference of Harmonisation
JC	Julius Centre
MAQC	MicroArray Quality Control
MERMAIDS	Multi-centre EuRopean study of MAjor Infectious Disease Syndromes
NHS	National Health Service
NRES	National Research Ethics Service
PCR	Polymerase Chain Reaction
PI	Principal Investigator
PIL	Participant/ Patient Information Leaflet
PREPARE	Platform for European Preparedness Against (Re-)emerging Epidemics
PSI	Pneumonia Severity Index / Fine Score
PSP	Project Specific Procedures
REC	Research Ethics Committee
RO	Research Online
R&D	NHS Trust R&D Department
REC	Research Ethics Committee
RSV	Respiratory Syncytial Virus

PREPARE | Multi-centre EuRopean study of MAjor Infectious Disease Syndromes

SOG	Study Operations Group
SOP	Standard Operating Procedure
SSC	Study Steering Committee
SST	Serum-separating Tube
WHO	World Health Organisation
WI	Work Instructions
WP3	Work Package 3

# 3. BACKGROUND AND RATIONALE

## 3.1 Background

PREPARE (Platform for European Preparedness Against (Re-)emerging Epidemics) is a European Commission funded network for harmonised large-scale clinical research studies on infectious diseases. The long-term aim is to establish a network that is prepared to rapidly respond to any severe infectious disease outbreak, providing real-time evidence for clinical management of patients and for informing public health responses. For more information on PREPARE please visit our website (www.prepare-europe.eu).

This study is part of the Multi-centre EuRopean study of MAjor Infectious Disease Syndromes (MERMAIDS), which comprises work package 3 (WP3) of the PREPARE platform.

# 3.2 Current limitations in understanding the pathogenesis of acute respiratory infections

Based on historic and recent pandemics or pandemic threats, as well as on knowledge of transmissibility and epidemiology, emerging or (re-)emerging pathogens causing acute respiratory infections (ARI) are considered the most likely candidates to cause the next pandemic.

There is a substantial body of knowledge on clinical risk factors for disease severity and outcome of ARIs. Validated clinical risk stratification tools, such as the Pneumonia Severity Index (PSI) (1) and CURB-65 score (2) predict outcomes and help to guide clinical decision making. Patient groups at risk for developing severe disease are well known, such as the elderly, patients with chronic pulmonary, cardiovascular or metabolic disease or immunocompromised patients. In national guidelines for prevention and treatment of ARI these risk groups are often combined.

However, the underlying pathophysiologic processes that determine the severity of ARI across the diversity of risk groups and pathogens likely differ and are not well understood. This means that within broad phenotypic 'risk groups' it is currently not possible to predict who is at increased risk of becoming severely ill. Consequently, there are no opportunities to tailor preventive and therapeutic interventions to individual risk. Personalised or precision medicine is becoming a reality in some areas of oncology, but has yet to enter infectious diseases (3). In patients that do become moderately or severely ill, there is an assumption that the underlying pathophysiological processes are the same, hence all patients will benefit equally from the same intervention, such as antivirals and immunomodulators. Increased insight into differences in underlying pathophysiological processes across clinical backgrounds and pathogens will open avenues for the development of predictive algorithms that anticipate severity at individual patient levels and direct strategies for individualized therapeutic interventions, hence improving clinical outcomes. Additionally, there may be

commonalities in host- and pathogen-related factors that determine outcome which could be used in generic diagnostic (e.g. distinguishing viral versus bacterial infection(4,5)) and therapeutic approaches. This could be of relevance to the next emerging novel respiratory pathogen, hence contributing to clinical preparedness for a new epidemic threat.

Analysis of the host gene expression profile (transcriptome) provides a high-resolution insight into host responses and pathophysiology, providing opportunities to understand the specific contributions of risk factors, comorbidities and pathogen-specific traits. As an example, human challenge studies using influenza virus, respiratory syncytial virus (RSV) and human rhinovirus (HRV) have indicated that peripheral blood gene expression profiles distinguish between specific viral aetiologies (6), and symptomatic and asymptomatic influenza virus infection (7,8), thus providing valuable insight into the development of clinical disease as well as avenues towards host-targeted approaches of aetiological diagnostics.

# 3.3 Rationale for study design

While experimental research remains essential to provide the foundations of our understanding of disease pathogenesis, detailed patient-oriented studies across the spectrum of clinical disease and aetiologies are needed to understand the complexities of 'real-life' pathogenesis of human infection, including the combined complex influences of age, comorbidities and co-infections with other pathogens in development of severe disease. This approach requires adequately sized and well defined cohorts with regards to age, presence of comorbidities and microbial aetiologies. To date, such patientoriented research in ARI has been limited to relatively small and heterogeneous groups of patients, in which data from patients of different ages with a diverse spectrum of comorbidities were usually combined (9–11). This makes identification of clinical background- or pathogen-specific pathophysiological pathways problematic if not impossible. In addition, most studies to date have focused on the severe end of the clinical spectrum (11-13). Although there are many genes that have increased expression regardless of the pathogen (14,15) differences are generally observed if the samples are taken early enough in the disease (16). There is also limited data on primary care patients and outpatients. Finally, many studies have investigated a single time point (11,13,17–21); analysing more time points is required to fully understand the dynamic nature of the host transcriptional profile (7).

Therefore, given the heterogeneity of clinical backgrounds and causative pathogens, the generation of meaningful insights into the relative contributions of host and pathogen factors to severe disease will require adequately sized cohorts of ARI patients across disease severities. The aim of the MERMAIDS ARI study is to establish such a cohort by enrolling sufficient numbers of patients across the most prevalent comorbidities (chronic pulmonary/cardiovascular/metabolic disease) and most prevalent pathogens (Influenza A, HRV, RSV and *Streptococcus pneumoniae*) with mild (community care) or moderately severe (hospitalised) ARI to have adequate statistical power to analyse differences in host response between these predefined subgroups. A small subset of ARI patients will progress to severe disease, as defined by the need for mechanical ventilation and/or death.

# 3.4 Study Aims

#### 3.4.1 Determinants of ARI disease severity

The primary aim of this study is to identify host and pathogen related determinants of disease severity of ARI. In this study we will include a prospectively defined and sufficiently sized patient cohort that will allow investigations of relative contributions of host and pathogen factors in development of mild, moderate and severe ARI. The sample size of this study is determined to provide adequate power to identify differences in RNA expression profiles between groups of patients with ARI stratified into groups by major categories of comorbidity (chronic pulmonary/cardiovascular/metabolic disease), and

PREPARE | Multi-centre EuRopean study of MAjor Infectious Disease Syndromes

the major causative pathogens (Influenza A, HRV, RSV and *Streptococcus pneumoniae*). Setting a high bar with regards to sample size, by basing our power calculation on the ability to detect differentially expressed genes between these predefined groups, will ensure the groups will be large enough to also compare less complex determinants of ARI severity, e.g. local and systemic innate and adaptive immune markers, and pathogen markers (e.g. pathogen load).

Our analysis will identify differentially expressed genes between patients with different comorbidities within and across ARI aetiologies and severities by combining a fold change assessment (>2-fold nominal change expression levels) combined with a p<0.05 correcting for multiple comparisons using the Benjamini-Hochberg False Discovery Rate (FDR) < 0.05 in accordance with guidelines from the MicroArray Quality Control (MAQC) group (22).

## 3.5 Aetiology, clinical management and outcomes of ARI across Europe

This study will be the largest comprehensive study to investigate and compare aetiology, pneumonia severity scores, clinical management and outcomes of adult ARI across Europe, in both primary and hospital care.

# 3.6 Diagnostic and prognostics markers

Analysis of transcriptional profiles will give us unique insight into determinants of disease severity, and it may also provide diagnostic and prognostic biomarkers. These may include classifier gene sets for aetiological diagnosis and prognosis, as well as composite algorithms using genetic markers, cytokine profiles, demographics, clinical backgrounds, and clinical parameters. Furthermore, we will be able to validate biomarkers and biomarker profiles that have already been determined in other studies, such as cytokine profiles from the MOSAIC study in patients with severe influenza infection (http://www1.imperial.ac.uk/mosaic/about/).

# 3.7 Pathophysiological mechanisms

Using a systems medicine approach, integrative analysis of pathogen and patient characteristics (e.g. clinical data on disease progression, respiratory microbiota, pathogen genotypes etc.) will be performed in relation to RNA transcriptional profiles. With pathway analyses and gene network clustering and correlations, we aim to identify commonalities in host- and pathogen-related factors. Such commonalities, if identified, can inform management in case of a future (severe) ARI or other epidemics of unknown origin.

# 4. STUDY DESIGN

International, multicentre, prospective observational study.

This study is designed to enrol sufficient subjects in each class of major pathogen (influenza virus, human rhinovirus, respiratory syncytial virus and *Streptococcus pneumoniae*) and comorbidity (no comorbidity, chronic pulmonary disease, chronic cardiovascular disease, and chronic metabolic disease) combination, in order to be adequately powered to detect 2 fold differences in host RNA transcriptome profiles between severity levels within each pathogen-comorbidity class.

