# 5. OBJECTIVES AND OUTCOME MEASURES

	Objectives	Outcome measures
Primary objective	Identify host and pathogen related	Differentially expressed host genes (≥ 2-fold
	determinants of severity of	difference in expression levels) as assessed
	community acquired acute	by RNA transcriptome microarray in
	respiratory infections (ARI) in adults.	hospitalised and primary care managed
		cases of ARI, stratified by pathogen* and
		comorbidity**.
		*Influenza virus, Human Rhinovirus, Respiratory
		Syncytial Virus, Streptococcus pneumoniae ; **No
		cardiovascular disease, chronic metabolic disease
		(diabetes)
Secondary	Describe the aetiology, clinical	In both groups:
objectives	management and outcomes of adult	Prevalence of detection of putative
	patients with community acquired	pathogens in respiratory tract samples.
	ARI, in both primary care and	
 
Proportion of cases receiving
 

	hospital care, across Europe.	antibiotics, antivirals, antifungals and/or
		immunomodulators.
		28 day mortality
		Additional in group 1 (primary care):
		
 
Proportion of cases requiring
 

		hospitalisation
		Additional in group 2 (hospitalised patients):
		
 
Severity of illness at enrolment as
 

		assessed by Pneumonia Severity Index
		(PSI) and CURB-65
		Proportion of cases requiring during
		admission: supplemental oxygen; non-
		invasive or invasive mechanical
		ventilation; extra-corporeal life support.
		Duration of invasive mechanical
		ventilation and extra-corporeal life
		support, if applicable
		Proportion of cases requiring Intensive
		Care Unit (ICU)/High Care Unit (HCU)
		admission
		Hospital - and ICU/HCU length of stay
		In-nospital mortality
Tertiary Objectives	To develop and validate prognostic	This is an exploratory objective. Some
	and diagnostic algorithms.	measures that could be included in
		algorithms are classifier gene sets based on
		host gene expression profiles, pathogen
		profiles, demographics, co-morbidities, risk
		factors, and clinical parameters. The
		diagnostic/prognostic algorithms will be
		evaluated for their ability to correctly
		diagnose infecting pathogen and/or predict
		adverse outcome in ARI.

PREPARE | Multi-centre EuRopean study of MAjor Infectious Disease Syndromes

13

Objectives	Outcome measures

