#### 8.1.2 Subgroup comparisons

We have performed sample size calculation on the ability to detect differentially expressed genes with a statistical power of at least 90% between all groups across the major pathogens (influenza virus, human rhinovirus, respiratory syncytial virus and *Streptococcus pneumoniae*), and major comorbidity groups (no comorbidity, chronic pulmonary disease, chronic cardiovascular disease, and chronic metabolic disease in hospitalised patients, and between primary care patients without comorbidities (Figure 1). Basing our power calculation on these subgroups will subsequently provide enough statistical power to detect differentially expressed genes in a number of other aetiologies across these comorbidities as well as for our secondary study objectives.

PREPARE | Multi-centre EuRopean study of MAjor Infectious Disease Syndromes

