# 8.2 Estimation of minimally required group sizes

We assume that the expression of each gene is normally distributed on the log scale and that the variance is the same in the different groups and thus the only difference between the groups is the mean. At an alpha of 0.05 and at an expected standard deviation of the gene intensity measurements on the base-two logarithmic scale of 0.7 (realistic for genes that are expressed at moderate to high levels), we expect to be able to detect 90% of >2 fold differentially expressed genes (i.e. an absolute effect size of 1 on a base-two logarithmic scale) between groups of 11 patients. These estimations are likely to be on the conservative side as we chose to err on the side of caution with regard to the chosen value for standard deviation. The calculation was based on the Affymetrix HG U133plus2 microarray platform, which contains 54,515 probe-sets.

	effect size in fold change			
power	2	1.75	1.5	
60%	5	8	15	
70%	7	10	18	
80%	8	12	23	
90%	11	16	31	
95%	13	20	38	

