#### 8.3.2 Number of primary care subjects needed

Based on the demographic and clinical data from the GRACE cohort (Genomics to combat Resistance against Antibiotics in Community-acquired LRTI in Europe, http://www.grace-lrti.org/) in primary care patients presenting with ARI, we can expect about 9.9% of patients with influenza A infection, 4.6% with RVS and 20.1% with HRV. We expect 50% (range 45-65%) of ARI patients in primary care not to have comorbidities. If we include 500 primary care patients we expect to find group sizes of at least 11 in patients without comorbidities infected with influenza virus A, HRV, RSV or *Streptococcus pneumoniae*.

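### Section 4 claims adequate power for severity contrasts in all 16 pathogen-comorbidity classes, but primary care is sized for only the four classes without comorbidity

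*Protocol*

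**What the plan says.** Section 4 sets the design target: the study is to be "adequately powered to detect 2 fold differences in host RNA transcriptome profiles between severity levels within each pathogen-comorbidity class". The classes are formed from influenza virus, rhinovirus (HRV), RSV and *S. pneumoniae*, crossed with no comorbidity and chronic pulmonary, cardiovascular and metabolic disease.

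Section 3.3 gives the levels of severity that the cohort is meant to power: "mild (community care) or moderately severe (hospitalised) ARI". The primary outcome in Section 5 matches this. It looks for differentially expressed genes in hospitalised and primary care cases, stratified by pathogen and comorbidity.

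Section 8 sizes something narrower. Section 8.1.2 covers every pathogen-comorbidity group among hospitalised patients, then adds "and between primary care patients without comorbidities". Section 8.3.2 makes the same restriction: "If we include 500 primary care patients we expect to find group sizes of at least 11 in patients without comorbidities" for each of the four pathogens. It gives no primary care prevalence for pulmonary, cardiovascular or metabolic disease.

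**The concern.** Section 4 promises power for 4 × 4 = 16 severity contrasts. A contrast between hospital and primary care needs patients on both sides. Section 8.3.1 provides the hospital side for all 16 classes, but Section 8.3.2 provides the primary care side only for the four without comorbidity. For the other 12, the protocol claims adequate power without a calculation behind it.

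This bears on the primary objective. RSV and *S. pneumoniae* are the least frequent of the four pathogens in primary care, so their comorbid cells will be small. A reader who trusts Section 4 could take an empty gene list in such a cell as evidence that severity leaves no transcriptional mark there.

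**Working it through.** **Inputs from the protocol.** Section 8.2: "At an alpha of 0.05 and at an expected standard deviation of the gene intensity measurements on the base-two logarithmic scale of 0.7", a 2-fold difference equal to 1 on that scale, 90% power, 11 per group. Section 8.3.2 and Table 6 (primary care): RSV 4.6%, *S. pneumoniae* 5.5%, influenza A 9.9%, HRV 20.1%; 50% (45–65%) without comorbidity, hence 50% (35–55%) with any. Tables 4 and 5 (hospital): RSV 4.6%, *S. pneumoniae* 6.9%; pulmonary 31.6%, cardiovascular 20.9%, metabolic 23.0%, none 35.8%. Sample sizes: 500 and 1,500 in Section 8.3; 750 and 2,250 in the Synopsis.

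**The plan's own figures reproduce.**
- Group size: 2 × 0.7² × (1.960 + 1.282)² = 10.3, rounded up to 11 (two-sided alpha, normal approximation). Power at 11 against 11 is 91.8% by z and 89.0% by t.
- Primary care without comorbidity at 500: 500 × prevalence × 0.5 gives influenza A 24.8, RSV 11.5, HRV 50.3, *S. pneumoniae* 13.8. All exceed 11.
- Hospital at 1,500: the smallest cell is HRV with cardiovascular disease, 1,500 × 0.039 × 0.209 = 12.2.

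**Comorbid primary care patients at 750.**
- RSV: 750 × 0.046 × 0.50 = 17.3 (12.1 at 35%, 19.0 at 55%).
- *S. pneumoniae*: 750 × 0.055 × 0.50 = 20.6 (14.4 to 22.7).

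Three cells of 11 need 33. Patients with two conditions count twice, but the hospital table implies only (31.6 + 20.9 + 23.0) / (100 − 35.8) = 75.5 / 64.2 = 1.18 conditions per comorbid patient. Even at 55% comorbid, that gives 19.0 × 1.18 = 22.4 and 22.7 × 1.18 = 26.8 cell places.

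**Single cells.** Reaching 11 at 750 needs a comorbidity prevalence of 11 / (750 × 0.046) = 31.9% for RSV or 11 / (750 × 0.055) = 26.7% for *S. pneumoniae*. The protocol gives no split, so two are assumed here: equal thirds of the 50%, and the hospital mix rescaled to 50% comorbid.

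| Expected cell count | Equal thirds, 750 | Equal thirds, 500 | Hospital mix, 750 (pulm./cardiov./metab.) |
|---|---|---|---|
| RSV | 5.8 | 3.8 | 8.5 / 5.6 / 6.2 |
| *S. pneumoniae* | 6.9 | 4.6 | 10.2 / 6.7 / 7.4 |
| Influenza A | 12.4 | 8.3 | 18.3 / 12.1 / 13.3 |
| HRV | 25.1 | 16.8 | 37.1 / 24.5 / 27.0 |

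**Power against the larger hospital cells.** At 2,250 the hospital cells (pulmonary/cardiovascular/metabolic) are RSV 32.7 / 21.6 / 23.8 and *S. pneumoniae* 49.1 / 32.4 / 35.7. Power = Φ(1 / [0.7 √(1/n₁ + 1/n₂)] − 1.96). For RSV with cardiovascular disease and equal thirds: 1 / [0.7 √(1/5.75 + 1/21.6)] = 3.04, and Φ(3.04 − 1.96) = 86% (83% by t).

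| Equal thirds, alpha 0.05 (z; t in brackets) | 750 / 2,250 | 500 / 1,500 |
|---|---|---|
| RSV | 86–88% (83–87%) | 70–73% (65–70%) |
| *S. pneumoniae* | 93–94% (91–93%) | 79–82% (76–80%) |

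With the rescaled hospital mix, z power at 750/2,250 is 96/86/89% for RSV and 99/92/94% for *S. pneumoniae*. At 500/1,500 it is 86/69/73% and 92/79/82%.

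**Effect of the FDR rule.** Section 8.4.1 also requires a Benjamini-Hochberg FDR below 0.05, which makes the per-gene threshold stricter. If that threshold lay between 0.01 and 0.001 (an assumption), t power at 750/2,250 with equal thirds would be 61–67% down to 29–36% for RSV, and 75–79% down to 45–52% for *S. pneumoniae*.

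**The case against.** The strongest reply is that 11 per group is a figure for two equal groups, whereas these contrasts are unequal. The large hospital cells recover much of the power: at 750/2,250 and nominal alpha, *S. pneumoniae* still exceeds 90% and RSV misses it by a few points. This stands. A reader who sees cells of six or seven might infer that the tests would be uninformative; at planned enrolment and nominal alpha the protocol's figures do not support that. But the protocol does not contain this calculation, and at the sample sizes of Section 8.3 the loss is substantial.

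Two other strong readings also fail. One is that no RSV or *S. pneumoniae* comorbid cell can reach 11. The required prevalences of 31.9% and 26.7% lie below the 50% with any comorbidity, and *S. pneumoniae* with pulmonary disease reaches 11.2 under the hospital mix at 55% comorbid, or 13.0 if hospital rates apply unscaled. What fails is all three cells together.

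The other is that Section 4 promises power for severe disease. Section 3.3 says "A small subset of ARI patients will progress to severe disease, as defined by the need for mechanical ventilation and/or death", but this follows the power statement as an observation. No section names ventilation or death as a powered level, and the primary outcome contrasts hospital with primary care.

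It can also be said that Section 8 states openly what was sized, and that Figure 1 is not legible in the text available. Both are fair, but neither reconciles Section 4 with Section 8.

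**Conclusion.** The power statement in Section 4 is wrong as written. Twelve of its 16 severity contrasts have no sample-size basis on the primary care side; this follows from the text alone.

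The shortfall in numbers falls mainly on RSV and *S. pneumoniae*. That all three comorbid cells cannot reach 11 at 750 rests on the stated prevalences and on overlap like that in the hospital table. RSV would need 33 / 17.3 = 1.9 conditions per comorbid patient, and *S. pneumoniae* 33 / 20.6 = 1.6. HRV cells are adequate throughout. Influenza A cells exceed 11 at 750 on central inputs but not all do at 500.

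The power figures rest on an assumed split, an SD of 0.7 and nominal alpha. On those terms the loss is moderate at 750/2,250 and marked at 500/1,500. It would be greater under the FDR criterion, by an amount that the protocol does not allow one to fix. The plan's 11 was itself set at nominal alpha.

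**What to change.** Restate Section 4 so that the powered severity contrasts, hospital against primary care, are the four pathogens in patients without comorbidity. Label the 12 comorbid severity contrasts exploratory.

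Alternatively, keep the wider claim and support it: state assumed primary care prevalences for the three comorbidities, and report unequal-group power for each comorbid contrast at the sample sizes actually planned.

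A per-pathogen model with setting, comorbidity and their interaction, including a pooled any-comorbidity contrast (about 17 RSV and 21 *S. pneumoniae* primary care patients at 750), may be added as a supplement. It should not replace the cell-wise contrasts, because Section 3.3 criticises earlier studies for combining diverse comorbidities.

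The first option costs a wording change, no extra patients and a narrower power claim. The second costs a short calculation and a source for the prevalences.
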